In the phase 1 study, administration of the drug was briefly suspended in 7 of 13 patients because of grade 3 abnormalities on liver function testing (n=2) or grade 3 or 4 mucositis (n=5). Liver-function abnormalities did not recur when the drug was re-started. The adverse event profile was similar to the expected toxicity observed in patients undergoing reduced intensity conditioned SCT without maraviroc. In addition, there were no viral or fungal infections other than asymptomatic reactivation of cytomegalovirus. The incidence of bacterial infections was not higher than the expected rate for a reduced intensity transplant. In conclusion, Maraviroc was generally well tolerated in this study [30,31].

Research Plan

The study continues seamlessly from one stage to the next and therefore does not have “phases” in the conventional sense. The initial part of the study will be a dose finding and feasibility study. The second stage of the study will involve administering the appropriate dose of Maraviroc to children as a prophylactic agent against acute graft versus host disease. Maraviroc will be added to standard GVHD prophylaxis of a calcineurin inhibitor (cyclosporine or tacrolimus), methylprednisolone, mycophenolate mofetil (MMF) or methotrexate. The study plan is described below.

Number of Subjects

We plan to enroll 65 patients over the course of approximately 5 years.

Selection

This study will be conducted at Cincinnati Children’s Hospital, in patients 2 years of age-40 years of age who are undergoing allogeneic stem cell transplant.

Eligibility

Inclusion Criteria

1. Ages- 2 years and \leq 40 years. For Phase I, the dose finding part of the study, enrollment will be limited to ages 2-12 years as adult dosing is already available and it is likely that a teenager metabolizes the drug similar to adults.

2. All diagnoses are eligible
3. Stem cell source must be marrow, peripheral blood stem cells or cord blood from an unrelated or related donor
4. All conditioning regimens are eligible.
5. Patient must be planned to receive a calcineurin inhibitor (cyclosporine or tacrolimus) together with steroid, methotrexate or mycophenolate mofetil as GVHD prophylaxis.
6. Willingness and ability to provide signed informed consent (including assent, for ages 11-17 years)

Exclusion Criteria

1. Documented anaphylaxis to Maraviroc
2. Ex vivo T depleted grafts

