3. Abnormal ALT (≥ 5 X ULN) on day -3. (This criterion is to be assessed at study enrollment, but it will be confirmed again prior to the first dose of maraviroc)
4. Individuals who are HIV positive will not be enrolled in the study.

Treatment Plan

Dose and schedule of Maraviroc administration-

Maraviroc administration will start on day -3 and will end on day +30 after stem cell transplant, making the total number of days of drug administration 34 days. Our goal is to have steady state Maraviroc concentrations before stem cell infusion (on day 0) and continuing during the period of engraftment. The day of planned stem cell infusion will be recorded as day zero. If the stem cell infusion is given over 2 days, the first of those 2 days will be considered as day zero. Maraviroc will be administered twice daily orally or via enteral tube. Maraviroc absorption is somewhat reduced with ingestion of a high-fat meal; however, it can be given with or without food.

Dosing of Maraviroc will be based on body surface area, which will be assessed prior to starting maraviroc. This is based on the current congenital HIV trial using Maraviroc. We hypothesize that the optimal dose and exposure (as measured by the area under the concentration-time curve; AUC) for GVHD prophylaxis will likely conform to the optimal dose for the congenital HIV population (Table1). However, we recognize that stem cell transplant patients are more highly catabolic and have significantly more

concomitant medications than HIV patients, so are aware that we may find important PK differences.

BSA (m ²)	Dose of Maraviroc to be administered orally
<0.22	40 mg bid
0.2-0.43	100 mg bid
0.44-0.72	200 mg bid
0.73-1.19	300 mg bid
1.20-1.30	300 mg bid
1.31-1.73	300 mg bid
>1.73	300 mg bid

Table 1. Dosing of Maraviroc based on BSA [32].

Drug interactions with maraviroc occur with strong CYP3A4 inducers and inhibitors so these may not be used during the period of administration of maraviroc.

Enzyme Inducers	Enzyme Inhibitors
Carbamazepine	Amiodarone
Phenobarbital	Clarithromycin/Erythromycin
Phenytoin	Azoles (Keto/ Itra/ Vori/Posaconazole)
Rifampin	Verapamil
Rifabutin	Diltiazem
St. John's Wart	Grapefruit Juice
	Antiretroviral medications

Table 2. List of concomitant medications (CYP3A4 inducers and inhibitors) not allowed at enrollment or during study treatment

Adverse effects of Maraviroc

For a complete list of adverse effects, please see page 18 of protocol [23].

Study design-

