For the first part of the study, where full AUC analysis will be performed to verify the dose, we anticipate initially enrolling 12 patients to achieve 12 dose verifications. Any patients who do not achieve a complete PK data profile (i.e. due to suboptimal dose or incomplete course of study drug) will be replaced to achieve 12 dose verifications. The total number of patients will still remain 65 (Phase I and Phase II). The age of enrollment for these patients will be limited to 2-12 years old. This age restriction has been imposed because adult dosing for maraviroc in the stem cell transplant setting has already been established and it is likely that teenagers metabolize the drug similar to adults. The second part of the study, where full AUC analysis will not be conducted, will enroll the remaining patients between the ages 2-40 years.

We will enroll eligible patients and maraviroc will be administered as per study rules. Area under the concentration-time curve (AUC) determination will be performed on days 0 +/- 3 days and 10 +/- 3 days to account for weekends, national holidays or clinical deterioration not allowing for scheduled blood draws on the specified days. PK analysis will be performed after the first 3 patients. As per our study design graph, this is not an "interim" analysis, but an analysis to verify PK target attainment which then will drive either further observation or dose escalation. See Figure 1.

[figure not shown]

Figure 1. Study design

Pharmacokinetic measurement and analysis-

Blood for PK will be collected on day 0 +/- 3 days and Day 10 +/- 3 days. Complete PK profile (full AUC) will be performed on these days (see time points below). Evaluation of maraviroc trough levels will also be done routinely on all patients on study on days 0,7,14 and 21 in order to collect additional PK data, verify compliance and allow for additional dose corrections if necessary.

Target AUC/12 hours= $\geq 100\text{ng/mL}$ (based on HIV data)

PK processing will be performed at University of North Carolina's Clinical Pharmacology and Analytical Chemistry Laboratory using mass spectrometer with HPLC separation.

Plasma Maraviroc concentration data will be analyzed by compartmental and non-compartmental analysis with the help of [name], Director of Pediatric Pharmacology Research Unit (PPRU) at CCHMC, and parameter estimates generated will include clearance, half-lives, and volume of distribution along with area under the curve (AUC).

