All patients in phase I treated at the established dose as well as patients treated at a lower dose yet achieve a therapeutic pharmacokinetic level will be included in further analysis. The historical incidence rate of GVHD in pediatric patients undergoing allogeneic stem cell transplantation with GVHD prophylaxis agent of a calcineurin inhibitor+ methylprednisolone is 16% (BMT 2012 data at CCHMC). Assuming the incidence rate for patients treated at the dose established in phase I is 6% then a sample size of evaluable 65 patients provides an 80% power of detecting a difference between this rate and the historical incidence rate. This sample size determination was computed using a two-sided binomial test.

The exact two-sided 95% confidence intervals for the day 100 incidence rate of grade GVHD will be reported. For time-to-event endpoints, e.g., overall survival and time to occurrence of GVHD, we will present Kaplan-Meier curves and corresponding survival p-values will be computed using log-rank tests. Demographic information such as age and race will be tabulated. Descriptive statistics, including means, standard deviations, and ranges for continuous parameters, as well as frequencies for categorical parameters, will be presented

Regulatory Issues-

The protocol and informed consent document for this study will be approved in writing by the Institutional Review Board (IRB) prior to any patient being registered on the study.

Changes to the protocol, as well as a change of study staff, must also be approved by the IRB. Records of the Institutional Review Board review and approval of all documents pertaining to this study must be kept on file by the investigator and are subject to FDA inspection at any time during the study.

Informed consent will be obtained prior to the treatment of participants.

This protocol will be performed under an investigator-initiated IND.

Study Monitoring and Auditing:

Monitoring and auditing procedures will be followed to ensure that the study is conducted, documented, and reported in accordance with the IRB approved protocol, all applicable federal regulations and guidelines, and applicable regulatory requirements of Cincinnati Children's Hospital Medical Center.

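### The 80% power is stated for 65 evaluable patients, but 65 is also total enrolment, with no allowance for non-evaluable patients; the effect on power depends on an alpha that is not stated

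*Combined protocol and SAP*

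**What the plan says.** The Statistical analysis section compares the day +100 GVHD rate with a fixed historical rate of 16%, assumes 6% on maraviroc, and states that "a sample size of evaluable 65 patients provides an 80% power" for that difference. It describes the calculation as a two-sided binomial test and plans an exact two-sided 95% confidence interval. It gives no alpha and does not define evaluable.

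Enrolment is set at the same number. Number of Subjects: "We plan to enroll 65 patients over the course of approximately 5 years". Study design, after saying that patients without a full PK profile will be replaced until there are 12 dose verifications: "The total number of patients will still remain 65 (Phase I and Phase II". The section on the time needed to complete the project says approximately 65.

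Three places bear on who is evaluable:

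- Statistical analysis carries forward into the later analysis "All patients in phase I treated at the established dose as well as patients treated at a lower dose yet achieve a therapeutic pharmacokinetic level". Phase I patients on a lower dose who stay below target are therefore left out.
- Dose escalation criteria: escalation requires 2 of the first 3 patients to be below the AUC target.
- Exclusion Criteria, item 3: the ALT criterion is assessed at enrolment, and "it will be confirmed again prior to the first dose of maraviroc".

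**The concern.** A power statement for 65 evaluable patients is met by enrolling 65 only if every enrolled patient ends up in the analysis set. The plan contains one rule that would take patients out, allows for none, and does not replace beyond 65.

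GVHD by day +100 is a primary endpoint, tested in a single arm against a fixed rate. With about 60 patients and low event rates, the test turns on whether 3, 4 or 5 events count as success, and that cut-off changes with the number analysed. If the set is undefined and alpha unstated, the classification of a single patient after the data are known could decide the result.

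**Working it through.** **Inputs.** From Statistical analysis: null rate 0.16, alternative 0.06, 65 evaluable patients, stated power 80%, two-sided binomial test. Alpha is not stated. Two levels are therefore used: lower-tail 5% (one-sided 5%, or two-sided 10%) and lower-tail 2.5% (two-sided 5%, which matches the planned 95% interval).

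**Formula.** For n patients, let c be the largest count with P(X ≤ c | n, 0.16) ≤ a, where a is the lower-tail level. Power is P(X ≤ c | n, 0.06).

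**Reproducing the plan's figure at n = 65.**

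- a = 0.05: P(X ≤ 5 | 65, 0.16) = 0.0401, so c = 5. Power = P(X ≤ 5 | 65, 0.06) = 80.6%. This reproduces 80%.
- a = 0.025: five events give 0.0401, which is too large; four give 0.0153, so c = 4. Power = 64.9%. This does not reproduce 80%.
- Normal approximation, a = 0.05: (0.10 − 1.645 × √(0.16 × 0.84/65)) / √(0.06 × 0.94/65) = 0.855, so power is 80.4%. This also reproduces 80%.
- Normal approximation, a = 0.025: 64.4%.

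Of these, only the lower-tail 5% calculations give the stated 80%.

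**Losses that follow from the plan's rule.** If escalation occurs, at least 2 of the first 3 patients were below target at the lower dose and fall outside the set: 65 − 2 = 63. If escalation does not occur, this rule removes nobody.

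**Exact power as n falls.**

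| n | a = 0.05: cut-off | Power | a = 0.025: cut-off | Power |
|---|---|---|---|---|
| 65 | ≤5 | 80.6% | ≤4 | 64.9% |
| 64 | ≤5 | 81.5% | ≤4 | 66.1% |
| 63 | ≤5 | 82.4% | ≤4 | 67.3% |
| 62 | ≤4 | 68.5% | ≤4 | 68.5% |
| 61 | ≤4 | 69.7% | ≤4 | 69.7% |
| 60 | ≤4 | 70.9% | ≤3 | 51.1% |
| 58 | ≤4 | 73.2% | ≤3 | 53.8% |

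**Where the steps come from.** At a = 0.05, five events have a lower-tail probability of 0.0493 in 63 patients and 0.0545 in 62, so the cut-off drops from 5 to 4. At a = 0.025, four events give 0.0244 in 61 patients and 0.0273 in 60, so it drops from 4 to 3. At either level, moving one patient in or out of the set can change whether a given event count rejects.

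**The same loss without discreteness.** With the normal approximation at a = 0.05 and n = 62: (0.10 − 1.645 × √(0.1344/62)) / √(0.0564/62) = 0.776, so power is 78.1%. That is 80.4 − 78.1 = 2.3 points lower, against 80.6 − 68.5 = 12.1 points with the exact test.

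**The case against.** The strongest reply is that the guaranteed loss does no harm. Escalation may never happen. If it does, the minimum of 2 exclusions leaves 63 patients, where exact power at lower-tail 5% is 82.4%, above the stated figure. That stands: reaching 62 or fewer needs further losses, and the documents give no rate for them.

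Two stronger readings are tempting.

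- A reader might infer that every replaced PK patient is lost to the efficacy analysis. The text does not support this. Replacement in Study design concerns incomplete PK profiles, while Statistical analysis keeps all phase I patients treated at the established dose.
- A reader might infer that losing about three patients costs 12 points of power. That holds only for an exact test at lower-tail 5%. The plan does not say whether its binomial test is exact or approximate, and the approximation loses about 2 points. At two-sided 5%, going from 65 to 62 patients raises exact power from 64.9% to 68.5%.

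Losses from the ALT recheck and before day +100 are also inferences. Nothing says whether a patient who fails the recheck uses one of the 65 places. Withdrawal is listed under early termination of study drug, and GVHD data to day +100 are collected as for all transplant patients, so stopping drug need not lose the endpoint.

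What survives is the mismatch itself: the evaluable number equals the enrolled number, evaluable is undefined, there is no allowance, and alpha is missing. The word approximately in the project-period section does not supply an allowance.

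**Conclusion.** The point holds in this form. The plan equates 65 enrolled with 65 evaluable, although its own rule would exclude at least 2 patients after an escalation and other losses are plausible.

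The size depends on alpha. At lower-tail 5%, the stated 80% survives one or two losses (81.5%, 82.4%). With an exact test it falls to 68.5% at 62 and 70.9% at 60; with a normal approximation it is about 78% at 62. At two-sided 5%, which the description of the test and the 95% interval suggest, power is 64.9% with all 65, 68.5% at 62 and 51.1% at 60. No number up to 65 delivers 80%, and the shortfall then comes first from alpha, not from attrition.

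The documents do not support saying that attrition alone defeats the power claim, or that any particular number of patients will be lost. These results assume true rates of 16% and 6%, as the plan does; how many losses go beyond the escalation rule is an assumption.

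**What to change.** Keep enrolment at 65 and amend the Statistical analysis section before the primary analysis:

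1. State alpha and sidedness, and whether the test is exact.
2. Define the primary GVHD analysis set. It could be every patient who received at least one dose of maraviroc, or the set the section now describes. Say how patients never dosed and patients lost before day +100 are handled.
3. Stop describing the 65 to be enrolled as 65 evaluable.
4. Restate power and give the exact rejection boundary for each n over a plausible evaluable range, labelled as an assumption, for example 58 to 65.

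This changes wording only and needs no extra patients. The cost is a less favourable stated power: over 58 to 65 patients the exact figure runs from 68.5% to 82.4% at lower-tail 5%, and from 51.1% to 69.7% at two-sided 5%.

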While data on Maraviroc blood levels are available from other studies, our patients are different from those previously studied, and these first cases will be of great value in determining the levels of drug we can achieve in this population

The time points of obtaining drug levels will be as follows:

- Hour 0- Pre maraviroc administration
- Hour 1 \pm 10 minutes - After maraviroc administration
- Hour 2 \pm 10 minutes- After maraviroc administration
- Hour 4 \pm 10 minutes- After maraviroc administration
- Hour 6 \pm 10 minutes- After Maraviroc administration
- Hour 8 \pm 10 minutes- After maraviroc administration
- Hour 12 \pm 20 minutes- After Maraviroc administration

Plasma concentration-time data will be explored graphically and the AUC will be estimated by non-compartmental analysis with the software package WinNonlin (Version 6.2, Pharsight Corporation, Palo Alto, CA). Full maraviroc PK profile and trough concentration data will be analyzed using a PK model-based Bayesian approach (MW/Pharm, MediWare, Groningen, the Netherlands).

Pharmacodynamic analysis will be performed in the laboratory using standard techniques.

Pharmacodynamic assessments will occur on days 0 +/-3 days and one time on day 14 +/- 3 days after stem cell infusion. Results will be available in a timely fashion to correlate with pharmacokinetic test results.

Dose escalation criteria-

Dose escalation will take place if all the requirements listed below are met:

1. The AUC/12 hours of the initial 2/3 patients is below 100 ng/ml

2. No more than 0 of 3 or 1/6 patients on the first dose level experience a dose limiting toxicity by day 30, defined as either-
 - a. Non-engraftment by day 30. Engraftment is defined as the first of three consecutive measurements of ANC>500/mcL over 3 or more days.
 - b. Grade 4 liver abnormalities, unless clearly related to stem cell transplant and not to the study drug, including but not limited to grade 4-5 liver toxicity due to hepatic veno-occlusive disease, grade 4-5 organ toxicities related to expected infections following stem cell transplant and their sequelae, or grade 4-5 toxicities related to graft versus host disease.

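### The day 0 ± 3 window lets the first full AUC be taken on the first day of dosing, and the written escalation rules do not say how such a profile is to be used

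*Combined protocol and SAP*

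**What the plan says.** **Dosing (Treatment Plan, dose and schedule).** "Maraviroc administration will start on day -3 and will end on day +30 after stem cell transplant". The protocol counts this as 34 days in all. Doses are given every 12 hours in effect: "Maraviroc will be administered twice daily orally or via enteral tube". The stated aim is: "Our goal is to have steady state Maraviroc concentrations before stem cell infusion (on day 0".

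**Sampling (Study design).** "Area under the concentration-time curve (AUC) determination will be performed on days 0 +/- 3 days and 10 +/- 3 days". The flexibility is meant for weekends, holidays and clinical deterioration. The study calendar and Table 6 repeat the ± 3 days for the day 0 profile. The sampling times start with a pre-dose sample, but no minimum number of earlier doses is required.

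**Use of the result.** PK is analysed after the first three patients, and the Study design section calls this "an analysis to verify PK target attainment which then will drive either further observation or dose escalation". The first escalation criterion is: "The AUC/12 hours of the initial 2/3 patients is below 100 ng/ml". The second is: "No more than 0 of 3 or 1/6 patients on the first dose level experience a dose limiting toxicity by day 30". Both must be met. The Statistical analysis section describes phase I as escalating until two of three patients exceed 100 ng/ml. None of these texts says whether the day 0 profile, the day 10 profile or both count.

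**Estimation (Pharmacokinetic measurement and analysis).** AUC is to be estimated by non-compartmental analysis. A model-based Bayesian analysis of profiles and troughs is also planned, but it is not linked to the escalation criterion.

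**The concern.** After the first dose there is no carry-over from earlier doses, so the AUC over the dosing interval is lower than it will be under continued dosing. The protocol's own aim of reaching steady state before day 0 implies that days -3 to -1 are a lead-in. Yet those days make up three of the seven in the first AUC window. A low reading on day -3 may reflect the sampling day and not the dose, and the error runs in one direction only, towards escalation.

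The reading matters beyond the visit itself. Attainment of the PK target is a primary end point. The dose established in phase I, in children aged 2 to 12, carries into the second stage. The Statistical analysis section keeps patients treated at a lower dose in further analysis only if they reached a therapeutic level, so a falsely low profile could also alter the analysis set.

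**Working it through.** **1. Timeline.** Counting day -3 to day +30 gives 30 - (-3) + 1 = 34 days, which reproduces the protocol's figure and confirms day -3 as the first dosing day. The first AUC window runs from 0 - 3 = day -3 to day +3; the second runs from day +7 to day +13.

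**2. Shortfall before steady state.** The documents give no half-life (it is to be estimated), so I assume a range. With linear one-compartment kinetics and 12-hour dosing, the AUC over 12 h after m earlier doses, divided by the steady-state AUC, is 1 - 2^(-(m+1) × 12/t½). Taking the first dose of each day, m = 0, 2, 4 and 6 on days -3, -2, -1 and 0.

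| Assumed t½ | day -3 | day -2 | day -1 | day 0 |
|---|---|---|---|---|
| 4 h | 88% | 99.8% | 100% | 100% |
| 8 h | 65% | 96% | 99% | 99.9% |
| 12 h | 50% | 88% | 97% | 99% |
| 16 h | 41% | 79% | 93% | 97% |
| 24 h | 29% | 65% | 82% | 91% |

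Example: 8 h on day -3 gives 1 - 2^(-1.5) = 0.646. These ratios do not depend on the units of the target. With slower oral absorption (assumed rate constants 0.5 to 1 per hour) the day -3 values are somewhat lower: 81% to 85% at 4 h and 57% to 61% at 8 h.

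**3. What a day -3 reading below 100 could hide.** Dividing 100 by the day -3 ratio, a patient would read low with a true steady-state value up to about 114 (4 h), 155 (8 h), 200 (12 h) or 247 (16 h).

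**4. Effect on the 2-of-3 rule.** The expected exposure and its spread are not in the documents either. Assume a log-normal AUC with CV 50%, so the log-scale SD is √ln(1.25) = 0.472, and a steady-state median of 150.

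- At steady state: p0 = Φ(ln(100/150)/0.472) = 0.195.
- Day -3, 4 h: median 150 × 0.875 = 131, p = 0.282.
- Day -3, 8 h: median 150 × 0.646 = 97, p = 0.526.

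If all three patients have the same probability p, the chance of at least two low readings is 3p² - 2p³. If one patient is profiled on day -3 and two at steady state, it is p0² + 2·p0·(1 - p0)·p.

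- All three at steady state: 3(0.195)² - 2(0.195)³ = 10%.
- One on day -3: 0.038 + 0.314 × 0.282 = 13% (4 h); 0.038 + 0.314 × 0.526 = 20% (8 h).
- All three on day -3: 19% (4 h); 54% (8 h).

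With a median of 300, same CV, the chance is below 0.1% at steady state. With all three on day -3 it is 0.1% (4 h) or 1.8% (8 h). A lower median or a longer half-life makes the effect larger: at median 150 and 12 h, all three on day -3, it is 82%.

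**The case against.** A day -3 profile would seldom be the only evidence. Escalation also needs the dose-limiting toxicity condition, assessed by day 30, and the second profile is due by day +13 at the latest. Patients without a complete PK data profile are replaced. The planned compartmental and Bayesian analyses could in principle predict steady-state exposure from an early profile. All of this stands, and it lowers the risk. But no text lets any of these override a low first profile, and the AUC itself is specified as non-compartmental.

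Day -3 is also an edge case. The nominal day is 0, the window is there for practical reasons, and the calendar has a separate day -3 column in which no full AUC is marked. If the half-life is 8 h or less, the shortfall by day -2 is at most about 4%, so only one of the seven window days matters much. That is a fair limit on how often the problem would arise; it does not exclude day -3.

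Figure 1, to which the Study design section refers for this decision, is not shown and may name the deciding profile. The observation is therefore about the written rules only.

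A reader might infer that the day 10 profile gives no protection unless it alone decides. That goes too far: requiring both profiles to be low, or a joint analysis, would also protect. Nor do the documents say that the target was defined for repeated dosing; they say only that it comes from HIV data. The case rests instead on the protocol's own steady-state aim.

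**Conclusion.** The point holds as a gap in the written rules. The first AUC window includes the first dosing day, no minimum number of earlier doses is set, and the visible escalation texts do not say which profile counts or what happens to one taken before steady state. A profile on day -3 is biased low, by about 12% at an assumed half-life of 4 h and 35% at 8 h, with larger shortfalls at longer half-lives.

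How far this moves the 2-of-3 rule cannot be settled from the documents, because half-life, expected exposure and variability are all assumed. A reader might take the 54% figure as the likely rate of unnecessary escalation. It is not. It needs all three patients on day -3, an 8 h half-life, and a median of 150 that the shortfall brings almost exactly onto the threshold (97 against 100). It is also the chance of meeting the PK criterion on first profiles alone, not of escalating. Nor do the documents show that the trial would in fact escalate on a first-dose AUC; they leave it possible. The correction is worth making because it is cheap and removes a bias with a known direction.

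**What to change.** Either open the first AUC window on day 0 (0 to +3 days), so that at least six doses have been taken if none is missed, or keep the present window and label any profile taken before day 0 as descriptive only. With six earlier doses the AUC is 97% to 100% of steady state for assumed half-lives of 4 to 16 h, and 91% at 24 h. The calendar already uses one-sided windows, at day +30 for example, and 0 to +3 still spans a long weekend.

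Then reconcile the dosing schedule, the Study design section with Figure 1, the escalation criteria and the Statistical analysis section, so that the PK criterion is applied only to steady-state profiles and the text says which of them count. If the model-based estimate is meant to be used for this decision, say so.

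The cost is slightly less scheduling freedom for one PK visit in about 12 patients. The change concerns sampling times and the use of the results; it proposes no dose and no clinical rule.
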